5.3.5 Procedures for Recording Adverse Events

Investigators should use correct medical terminology/concepts when recording adverse events on the Adverse Event eCRF. Avoid colloquialisms and abbreviations.

Only one adverse event term should be recorded in the event field on the Adverse Event eCRF.

For the purposes of reporting events of infection and inflammation, see examples of terms and definitions to be used:

- Iritis: the presence of inflammatory cells in the AC
 - The presence of aqueous flare alone will not constitute iritis but should be documented as an AC flare for adverse event reporting purposes.
- Iridocyclitis: the presence of inflammatory cells in both the aqueous and vitreous
- Vitritis: the presence of active inflammation in the vitreous, demonstrated by the presence of inflammatory cells
 - Active inflammation in the vitreous should be clinically differentiated from cellular debris from prior episodes of inflammation, hemorrhage, or other causes.
- Endophthalmitis: diffuse intraocular inflammation predominantly involving the vitreous cavity but also involving the AC, implying a suspected underlying infectious cause

If possible, a sample for culture should be taken prior to initiating antibiotic treatment for presumed endophthalmitis. Results of bacterial or fungal cultures, treatment given, and final ophthalmologic outcome should also be provided in the details section of the Adverse Event eCRF.

Note: Trace benign, aqueous pigmented cells visible on slit lamp examination that are caused by dilation and are not red blood cells or white blood cells or the result of any ocular disorder should not be recorded as an adverse event.

5.3.5.1 Diagnosis Versus Signs and Symptoms

A diagnosis (if known) should be recorded on the Adverse Event eCRF rather than individual signs and symptoms (e.g., record only liver failure or hepatitis rather than jaundice, asterixis, and elevated transaminases). However, if a constellation of signs and/or symptoms cannot be medically characterized as a single diagnosis or syndrome at the time of reporting, each individual event should be recorded on the Adverse Event eCRF. If a diagnosis is subsequently established, all previously reported adverse events based on signs and symptoms should be nullified and replaced by one adverse event report based on the single diagnosis, with a starting date that corresponds to the starting date of the first symptom of the eventual diagnosis.

5.3.5.2 Adverse Events That Are Secondary to Other Events

In general, adverse events that are secondary to other events (e.g., cascade events or clinical sequelae) should be identified by their primary cause, with the exception of severe or serious secondary events. A medically significant secondary adverse event that is separated in time from the initiating event should be recorded as an independent event on the Adverse Event eCRF. For example:

- If vomiting results in mild dehydration with no additional treatment in a healthy adult, only vomiting should be reported on the eCRF.
- If vomiting results in severe dehydration, both events should be reported separately on the eCRF.
- If a severe gastrointestinal hemorrhage leads to renal failure, both events should be reported separately on the eCRF.
- If dizziness leads to a fall and consequent fracture, all three events should be reported separately on the eCRF.
- If neutropenia is accompanied by an infection, both events should be reported separately on the eCRF.

All adverse events should be recorded separately on the Adverse Event eCRF if it is unclear as to whether the events are associated.

5.3.5.3 Persistent or Recurrent Adverse Events

A persistent adverse event is one that extends continuously, without resolution, between patient evaluation timepoints. Such events should only be recorded once on the Adverse Event eCRF. The initial severity (intensity or grade) of the event will be recorded at the time the event is first reported. If a persistent adverse event becomes more severe, the most extreme severity should also be recorded on the Adverse Event eCRF. If the event becomes serious, it should be reported to the Sponsor immediately (i.e., within ≤24 hours after learning that the event became serious; see Section 5.4.2 for

reporting instructions). The Adverse Event eCRF should be updated by changing the event from "non-serious" to "serious," providing the date that the event became serious, and completing all data fields related to serious adverse events.

A recurrent adverse event is one that resolves between patient evaluation timepoints and subsequently recurs. Each recurrence of an adverse event should be recorded as a separate event on the Adverse Event eCRF.

5.3.5.4 Abnormal Laboratory Values

Not every laboratory abnormality qualifies as an adverse event. A laboratory test result must be reported as an adverse event if it meets any of the following criteria:

- Is accompanied by clinical symptoms
- Results in a change in study treatment (e.g., dosage modification, treatment interruption, or treatment discontinuation)
- Results in a medical intervention (e.g., potassium supplementation for hypokalemia) or a change in concomitant therapy
- Is clinically significant in the Investigator's judgment

It is the Investigator's responsibility to review all laboratory findings. Medical and scientific judgment should be exercised in deciding whether an isolated laboratory abnormality should be classified as an adverse event.

If a clinically significant laboratory abnormality is a sign of a disease or syndrome (e.g., alkaline phosphatase and bilirubin 5×upper limit of normal [ULN] associated with cholestasis), only the diagnosis (i.e., cholestasis) should be recorded on the Adverse Event eCRF.

If a clinically significant laboratory abnormality is not a sign of a disease or syndrome, the abnormality itself should be recorded on the Adverse Event eCRF, along with a descriptor indicating whether the test result is above or below the normal range (e.g., "elevated potassium," as opposed to "abnormal potassium"). If the laboratory abnormality can be characterized by a precise clinical term per standard definitions, the clinical term should be recorded as the adverse event. For example, an elevated serum potassium level of 7.0 mEg/L should be recorded as "hyperkalemia."

Observations of the same clinically significant laboratory abnormality from visit to visit should only be recorded once on the Adverse Event eCRF (see Section 5.3.5.3 for details on recording persistent adverse events).

5.3.5.5 Abnormal Vital Sign Value

Not every vital sign abnormality qualifies as an adverse event. A vital sign result must be reported as an adverse event if it meets any of the following criteria:

Is accompanied by clinical symptoms

- Results in a change in study treatment (e.g., dosage modification, treatment interruption, or treatment discontinuation)
- Results in a medical intervention or a change in concomitant therapy
- Is clinically significant in the Investigator's judgment

It is the investigator's responsibility to review all vital sign findings. Medical and scientific judgment should be exercised in deciding whether an isolated vital sign abnormality should be classified as an adverse event.

If a clinically significant vital sign abnormality is a sign of a disease or syndrome (e.g., high BP), only the diagnosis (i.e., hypertension) should be recorded on the Adverse Event eCRF.

Observations of the same clinically significant vital sign abnormality from visit to visit should only be recorded once on the Adverse Event eCRF (see Section 5.3.5.3 for details on recording persistent adverse events).

5.3.5.6 Abnormal Liver Function Tests

The finding of an elevated ALT or AST ($>3 \times ULN$) in combination with either an elevated total bilirubin ($>2 \times ULN$) or clinical jaundice in the absence of cholestasis or other causes of hyperbilirubinemia is considered to be an indicator of severe liver injury (as defined by Hy's Law). Therefore, Investigators must report as an adverse event the occurrence of either of the following:

- Treatment-emergent ALT or AST > 3 × ULN in combination with total bilirubin > 2 × ULN
- Treatment-emergent ALT or AST > 3 × ULN in combination with clinical jaundice

The most appropriate diagnosis or (if a diagnosis cannot be established) the abnormal laboratory values should be recorded on the Adverse Event eCRF (see Section 5.3.5.1) and reported to the Sponsor immediately (i.e., within \leq 24 hours after learning of the event), either as a serious adverse event or an adverse event of special interest (see Section 5.4.2).

5.3.5.7 Deaths

All deaths that occur during the protocol-specified adverse event reporting period (see Section 5.3.1), regardless of relationship to study drug, must be recorded on the Adverse Event eCRF and immediately reported to the Sponsor (see Section 5.4.2).

Death should be considered an outcome and not a distinct event. The event or condition that caused or contributed to the fatal outcome should be recorded as the single medical concept on the Adverse Event eCRF. Generally, only one such event should be reported. If the cause of death is unknown and cannot be ascertained at the time of reporting, "unexplained death" should be recorded on the Adverse Event eCRF. If the cause of death later becomes available (e.g., after autopsy), "unexplained death" should

be replaced by the established cause of death. The term "sudden death" should not be used unless combined with the presumed cause of death (e.g., "sudden cardiac death").

Deaths that occur after the adverse event reporting period should be reported as described in Section 5.6.

5.3.5.8 Preexisting Medical Conditions

A preexisting medical condition is one that is present at the screening visit for this study. Such conditions should be recorded on the General Medical History and Baseline Conditions eCRF

A preexisting medical condition should be recorded as an adverse event only if the frequency, severity, or character of the condition worsens during the study. When recording such events on the Adverse Event eCRF, it is important to convey the concept that the preexisting condition has changed by including applicable descriptors (e.g., "more frequent headaches").

5.3.5.9 Lack of Efficacy or Worsening of Diabetic Macular Edema or Diabetic Retinopathy in the Study Eye

Medical occurrences or symptoms of deterioration that are anticipated as part of study eye DME or DR should be recorded as an adverse event if judged by the Investigator to have unexpectedly worsened in severity or frequency or changed in nature at any time during the study. When recording an unanticipated worsening of study eye DME or DR on the Adverse Event eCRF, it is important to convey the concept that the condition has changed by including applicable descriptors (e.g., "accelerated worsening diabetic macular edema"). The expedited reporting requirements for associated sight threatening events (listed in the Section 5.2.3) will apply.

5.3.5.10 Hospitalization or Prolonged Hospitalization

Any adverse event that results in hospitalization (i.e., inpatient admission to a hospital) or prolonged hospitalization should be documented and reported as a serious adverse event (per the definition of serious adverse event in Section 5.2.2), except as outlined below.

An event that leads to hospitalization under the following circumstances should not be reported as an adverse event or a serious adverse event:

 Hospitalization for a preexisting condition, provided that all of the following criteria are met:

The hospitalization was planned prior to the study or was scheduled during the study when elective surgery became necessary because of the expected normal progression of the disease.

The patient has not experienced an adverse event.

An event that leads to hospitalization under the following circumstances is not considered to be a serious adverse event, but should be reported as an adverse event instead:

 Hospitalization that was necessary because of patient requirement for outpatient care outside of normal outpatient clinic operating hours.

5.3.5.11 Cases of Accidental Overdose or Medication Error

Accidental overdose and medication error (hereafter collectively referred to as "special situations"), are defined as follows:

- Accidental overdose: accidental administration of a drug in a quantity that is higher than the assigned dose
- Medication error: accidental deviation in the administration of a drug
 In some cases, a medication error may be intercepted prior to administration of the drug.

Special situations are not in themselves adverse events, but may result in adverse events. Each adverse event associated with a special situation should be recorded separately on the Adverse Event eCRF. If the associated adverse event fulfills seriousness criteria or qualifies as an adverse event of special interest, the event should be reported to the Sponsor immediately (i.e., within ≤ 24 hours after learning of the event; see Section 5.4.2). For faricimab, adverse events associated with special situations should be recorded as described below for each situation:

- Accidental overdose: Enter the adverse event term. Check the "Accidental overdose" and "Medication error" boxes.
- Medication error that does not qualify as an overdose: Enter the adverse event term. Check the "Medication error" box.
- Medication error that qualifies as an overdose: Enter the adverse event term.
 Check the "Accidental overdose" and "Medication error" boxes.

In addition, all special situations associated with faricimab, regardless of whether they result in an adverse event, should be recorded on the Adverse Event eCRF as described below:

- Accidental overdose: Enter the drug name and "accidental overdose" as the event term. Check the "Accidental overdose" and "Medication error" boxes.
- Medication error that does not qualify as an overdose: Enter the name of the drug administered and a description of the error (e.g., wrong dose administered, wrong dosing schedule, incorrect route of administration, wrong drug, expired drug administered) as the event term. Check the "Medication error" box.
- Medication error that qualifies as an overdose: Enter the drug name and "accidental overdose" as the event term. Check the "Accidental overdose" and "Medication error" boxes. Enter a description of the error in the additional case details.

 Intercepted medication error: Enter the drug name and "intercepted medication error" as the event term. Check the "Medication error" box. Enter a description of the error in the additional case details.

As an example, an accidental overdose that resulted in a headache would require two entries on the Adverse Event eCRF, one entry to report the accidental overdose and one entry to report the headache. The "Accidental overdose" and "Medication error" boxes would need to be checked for both entries.

To ensure the safety of study patients, an Emergency Medical Call Center will be available 24 hours per day, 7 days per week, in case the above-listed contacts cannot be reached. The Emergency Medical Call Center will connect the Investigator with an Emergency Medical Contact, provide medical translation service if necessary, and track all calls. Contact information, including toll-free numbers for the Emergency Medical Call Center, will be distributed to Investigators.

5.4.2 Reporting Requirements for Serious Adverse Events and Adverse Events of Special Interest

5.4.2.1 Events That Occur prior to Study Drug Initiation

After informed consent has been obtained but prior to initiation of study drug, only serious adverse events caused by a protocol-mandated intervention should be reported. The paper Clinical Trial Adverse Event/Special Situations Form provided to Investigators should be completed and submitted to the Sponsor or its designee immediately (i.e., within ≤ 24 hours after learning of the event), either by faxing or scanning and emailing the form using the fax number or email address provided to Investigators.

5.4.2.2 Events That Occur after Study Drug Initiation

After initiation of study drug, serious adverse events and adverse events of special interest will be reported until SFV (\geq 28 to < 35 days from last study treatment). Investigators should record all case details that can be gathered immediately (i.e., within 24 hours after learning of the event) on the Adverse Event eCRF and submit the report via the electronic data capture (EDC) system. A report will be generated and sent to Roche Safety Risk Management by the EDC system.

In the event that the EDC system is unavailable, the paper Clinical Trial Adverse Event/Special Situations Form provided to Investigators should be completed and submitted to the Sponsor or its designee immediately (i.e., within ≤ 24 hours after learning of the event), either by faxing or scanning and emailing the form using the fax number or email address provided to Investigators. Once the EDC system is available, all information will need to be entered and submitted via the EDC system.

Instructions for reporting post-study adverse events are provided in Section 5.6.

5.4.3 Reporting Requirements for Pregnancies

5.4.3.1 Pregnancies in Female Patients

Female patients of childbearing potential will be instructed $through\ the\ Informed\ Consent\ Form\ to\ immediately\ inform\ the\ investigator\ if\ they\ become\ pregnant\ during\ the\ study\ or\ within\ 3\ months\ after\ the\ final\ dose\ of\ study\ drug.\ A\ paper\ Clinical\ Trial\ Pregnancy\ Reporting\ Form\ should\ be\ completed\ and\ submitted\ to\ the\ Sponsor\ or\ its\ designee\ immediately\ (i.e.,\ within\ <math>\le 24\ hours\ after\ learning\ of\ the\ pregnancy),\ either\ by\ faxing\ or\ scanning\ and\ emailing\ the\ form\ using\ the\ fax\ number\ or\ email\ address\ provided\ to\ investigators.\ Pregnancy\ should\ not\ be\ recorded\ on\ the\ Adverse\ Event\ eCRF.\ The\ investigator\ should\ discontinue\ study\ drug\ and\ counsel\ the\ patient,\ discussing\ the\ risks\ of\ the\ pregnancy\ and\ the\ possible\ effects\ on\ the\ fetus.\ Monitoring\ of\ the\ patient\ should\ continue\ until\ conclusion\ of\ the\ pregnancy.\ Any\ serious\ adverse\ events\ associated\ with\ the\ pregnancy\ (e.g.,\ an\ event\ in\ the\ fetus,\ an\ event\ in\ the\ mother\ during\ or\ after\ the\ pregnancy,\ or\ a\ congenital\ anomaly/birth\ defect\ in\ the\ child)\ should\ be\ reported\ on\ the\ Adverse\ Event\ eCRF.\ In\ addition,\ the\ Investigator\ will\ submit\ a\ Clinical\ Trial\ Pregnancy\ Reporting\ Form\ when\ updated\ information\ on\ the\ course\ and\ outcome\ of\ the\ pregnancy\ becomes\ available.$

5.4.3.2 Abortions

A spontaneous abortion should be classified as a serious adverse event (as the Sponsor considers abortions to be medically significant), recorded on the Adverse Event eCRF, and reported to the Sponsor immediately (i.e., within \leq 24 hours after learning of the event; see Section 5.4.2).

If a therapeutic or elective abortion was performed because of an underlying maternal or embryofetal toxicity, the toxicity should be classified as a serious adverse event, recorded on the Adverse Event eCRF, and reported to the Sponsor immediately (i.e., within ≤24 hours after learning of the event; see Section 5.4.2). A therapeutic or elective abortion performed for reasons other than an underlying maternal or embryofetal toxicity is not considered an adverse event.

All abortions should be reported as pregnancy outcomes on the paper Clinical Trial Pregnancy Reporting Form.

5.4.3.3 Congenital Anomalies/Birth Defects

Any congenital anomaly/birth defect in a child born to a female patient exposed to study drug should be classified as a serious adverse event, recorded on the Adverse Event eCRF, and reported to the Sponsor immediately (i.e., within \leq 24 hours after learning of the event; see Section 5.4.2).

5.5 FOLLOW-UP OF PATIENTS AFTER ADVERSE EVENTS

5.5.1 Investigator Follow-Up

The Investigator should follow each adverse event until the event has resolved to baseline grade or better, the event is assessed as stable by the Investigator, the patient is lost to

follow-up, or the patient withdraws consent. Every effort should be made to follow all serious adverse events considered to be related to study drug or trial-related procedures until a final outcome can be reported.

During the study period, resolution of adverse events (with dates) should be documented on the Adverse Event eCRF and in the patient's medical record to facilitate source data verification.

All pregnancies reported during the study should be followed until pregnancy outcome.

5.5.2 Sponsor Follow-Up

For serious adverse events, adverse events of special interest, and pregnancies, the Sponsor or a designee may follow-up by telephone, fax, email, and/or a monitoring visit to obtain additional case details and outcome information (e.g., from hospital discharge summaries, consultant reports, autopsy reports) in order to perform an independent medical assessment of the reported case.

5.6 ADVERSE EVENTS THAT OCCUR AFTER THE ADVERSE EVENT REPORTING PERIOD

The Sponsor should be notified if the Investigator becomes aware of any serious adverse event that occurs after the end of the adverse event reporting period (until the SFV [\geq 28 to <35 days from the last study treatment]), if the event is believed to be related to prior study drug treatment. These events should be reported through use of the Adverse Event eCRF. However, if the EDC system is not available, the investigator should report these events directly to the Sponsor or its designee, either by faxing or by scanning and emailing the paper Clinical Trial Adverse Event/Special Situations Form using the fax number or email address provided to Investigators.

5.7 EXPEDITED REPORTING TO HEALTH AUTHORITIES, INVESTIGATORS, INSTITUTIONAL REVIEW BOARDS, AND ETHICS COMMITTEES

The Sponsor will promptly evaluate all serious adverse events and adverse events of special interest against cumulative product experience to identify and expeditiously communicate possible new safety findings to Investigators, IRBs, ECs, and applicable health authorities based on applicable legislation.

To determine reporting requirements for single adverse event cases, the Sponsor will assess the expectedness of these events using the following reference document for IMPs:

RO6867461 (faricimab) Investigator's Brochure

The Sponsor will compare the severity of each event and the cumulative event frequency reported for the study with the severity and frequency reported in the reference document.

Reporting requirements will also be based on the investigator's assessment of causality and seriousness, with allowance for upgrading by the Sponsor as needed.

6. STATISTICAL CONSIDERATIONS AND ANALYSIS PLAN

All exploratory outcomes will be analyzed in the modified intent-to-treat (mITT) population. The mITT population is defined as all patients enrolled in the study that received any amount of study medication. Safety analyses will be performed on the safety-evaluable population, which consists of all patients who receive any amount of study medication. Detailed specifications of the statistical methods will be described in the Statistical Analysis Plan (SAP).

6.1 DETERMINATION OF SAMPLE SIZE

In this exploratory study, the sample size is based on practical considerations. Approximately 80 patients will be enrolled in the study. With a minimum of 40 patients, there is approximately 80% power to demonstrate that a correlation of 0.4 is statistically significantly different from 0 (alpha=0.05). Sample size was *calculated* to 80 to account (adjust) for exploratory multivariate analyses that may be performed to model clinical outcomes based on multiple AH biomarkers.

The Sponsor may increase the sample size up to 100 patients, to compensate for those patients who completed the study without having a full set of Day 1 (baseline) and Day 112 visit analyzable* AH samples collected. The aim of this increase is to achieve 60 patients with analyzable* Day 1 (baseline) and Day 112 visit AH samples. The Sponsor may decide to stop the enrollment as soon as the target of 60 analyzable* sets of AH samples is reached.

* Analyzable refers to the AH samples with no major deviations that will be analyzed by at least one specialty laboratory.

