4. STATISTICAL METHODS

For continuous variables, descriptive statistics (e.g., number of patients [n], mean, standard deviation [SD], median, 25th and 75th percentiles, minimum, maximum) will be calculated and summarized.

For categorical variables, the number and percentage in each category will be displayed.

Statistical methods for exploratory endpoints are detailed in the Exploratory Analyses section below.

Unless otherwise specified, statistical tests will be two-sided and the statistical significance level will be 5%. Corresponding 95% CIs will be presented as appropriate. Although multiple statistical tests may be conducted, due to the exploratory nature of the study no adjustments to the Type 1 error rate for multiplicity will be made.

The analyses outlined in this SAP supersede those specified in the protocol.

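### The stated power of about 80% for r = 0.4 with 40 patients is about 73–74% at the SAP's two-sided 5% level; 80% needs 46–47 patients

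*Protocol*

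**What the plan says.** Protocol 6.1 describes the sample size as a practical choice of about 80 patients and then gives one power statement: "With a minimum of 40 patients, there is approximately 80% power to demonstrate that a correlation of 0.4 is statistically significantly different from 0", at alpha 0.05. The same sentence stands in the protocol synopsis, in SAP 2.3, and in the synopsis reproduced in SAP Appendix 1. Sidedness is not given in any of them.

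SAP section 4 sets the general rule: "Unless otherwise specified, statistical tests will be two-sided and the statistical significance level will be 5" percent. It adds that there is no adjustment for multiplicity, so each test keeps its 5% level.

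Protocol 6.4 allows Pearson or Spearman coefficients, depending on the data type, with no imputation of missing data.

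On the number of samples, Protocol 6.1 allows an increase to 100 patients and says: "The aim of this increase is to achieve 60 patients with analyzable* Day 1 (baseline) and Day 112 visit AH samples". SAP 2.3 reports that the sample size was raised to 99. No power is given for the 60 sets.

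**The concern.** A correlation of 0.4 with 40 pairs is a standard calculation, and 80% looks too high for a two-sided 5% test. The wording "a correlation of 0.4 is statistically significantly different from 0" itself describes a two-sided alternative, which agrees with the SAP's default.

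This is the trial's only power statement and the only quantitative support for any minimum number of patients. If the figure is too high, the plan understates the risk of missing a true correlation of 0.4. A reader would also take 40 pairs as adequate when they are not, by the plan's own 80% standard. Analyses with fewer than 60 pairs are possible. A sample counts as analyzable if at least one specialty laboratory will analyze it, so 60 sets need not mean 60 pairs on every assay platform. Global protein and metabolite analysis depends on the volume collected (Protocol 4.5.7.1), and swept-source OCT is done only at sites that have it (Protocol 4.5.5).

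**Working it through.** **Inputs**
- n = 40, r = 0.4 against 0, alpha = 0.05, stated power about 80%: Protocol 6.1 and SAP 2.3.
- Two-sided test, no multiplicity adjustment: SAP section 4.
- Target of 60 complete sets and about 80 patients enrolled: Protocol 6.1.

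**Trying to reproduce the stated 80%**

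Fisher's z: power = Φ(atanh(r)·√(n − 3) − z), with z = 1.960 two-sided or 1.645 one-sided. The opposite tail is negligible.

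- atanh(0.4) = 0.4236 and √37 = 6.083, so the product is 2.577.
- Two-sided: 2.577 − 1.960 = 0.617, so power = **73.1%**.
- One-sided 5%: 2.577 − 1.645 = 0.932, so power = 82.4%.

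The exact distribution of r under bivariate normality, with two-sided critical |r| = 0.312, gives **74.2%**. A simulation of 400,000 data sets gives 74.3%. The one-sided exact figure is 83.4%.

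The most generous two-sided alternative tried was a noncentral t that treats one variable as fixed. It gives 74.6–76.7%, depending on the noncentrality convention. No two-sided method reaches 80% at n = 40.

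**Patients needed for 80%**

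Fisher's z: n = ((z_α + z_β)/atanh(r))² + 3.

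- Two-sided: ((1.960 + 0.842)/0.4236)² + 3 = 46.7, so 47.
- One-sided: ((1.645 + 0.842)/0.4236)² + 3 = 37.4, so 38.

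**Two-sided power for r = 0.4 at other sizes**

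| n | Fisher's z | Exact |
|---|---|---|
| 40 | 73.1% | 74.2% |
| 45 | 78.4% | 79.3% |
| 46 | 79.3% | 80.2% |
| 47 | 80.2% | 81.1% |
| 60 | 89.2% | 89.7% |
| 80 | 96.1% | 96.2% |

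The exact method therefore needs 46 patients and Fisher's z needs 47: 6 to 7 more than 40, or 15–18%. With n held at 40, 80% power is reached only for r of about 0.43.

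**Spearman**

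On bivariate-normal data with a Pearson correlation of 0.4, simulated two-sided power at n = 40 is 68.4% (40,000 runs). The population Spearman correlation is then 0.385, so this is not the same effect. With the Spearman correlation itself at 0.4, variance approximations give 69.8–70.6% and a simulation gives 72.5%. All fall below the Pearson figure.

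**The case against.** The sample-size sections give only alpha = 0.05; the two-sided reading comes from a default in SAP section 4 that yields to anything specified otherwise. SAP 4.4 also sends the biomarker, imaging and clinical association analyses to a separate document, which is not available here. A one-sided 5% calculation needs 37–38 patients, which could have been rounded to a minimum of 40 and about 80%, so an unstated one-sided assumption is a plausible origin. This stands as an explanation of where the figure came from. It does not make the figure right: nothing in either document departs from the default, and the sentence describes a difference from 0 without a direction.

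The second argument is about weight. The sample size is said to be practical, and the 80 is attributed to multivariate modelling. The 40 is not used as a stopping rule, an enrolment floor or an analysis threshold; the SAP's subgroup minimum is 30. The documents do not say that any analysis will end with about 40 pairs. Correlations are to be judged by magnitude and plots. All of this is fair and limits the consequence. Likewise, giving no power for the 60 sets is an omission in reporting, not an arithmetic error. None of it changes the power at 40 patients, which the text itself calls a minimum.

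**Conclusion.** The power statement is wrong as written. At the two-sided 5% level, 40 patients give 73–74% power for a Pearson correlation of 0.4. That is 6–7 percentage points below the claim, and too large a gap for the word approximately to cover. Type II error is 26–27% instead of 20%, and 80% power needs 46–47 patients.

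This rests on the SAP's two-sided default applying to the correlation tests, on bivariate normality for the exact figure, and on no multiplicity adjustment, as the SAP states. Spearman tests on bivariate-normal data would widen the shortfall.

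The consequence is modest. One pairwise correlation of 0.4 has 89–90% power at 60 sets and about 96% at 80, so neither the enrolment nor the sample target is in doubt.

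**What to change.** Replace the sentence in Protocol 6.1, the synopsis and SAP 2.3 (and the synopsis copy in SAP Appendix 1) with wording such as: *With 40 patients there is about 74% power (Pearson correlation, two-sided alpha 0.05) to show that a correlation of 0.4 differs from 0; 46–47 patients are needed for 80%; the target of 60 analyzable sets of aqueous humor samples gives about 90%.*

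If the calculation was one-sided, the sponsor should instead state that, justify the departure from SAP section 4, and give the matching figure of 82–83% at 40 patients.

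SAP 2.3 already reports the increase to 99 patients, so the correction should also carry into the separate association-analysis document and the study report. The cost is one sentence in each place and a less favourable figure at 40 patients. No extra patients are needed, and the restated text supports the real target of 60 better than the present one does.
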